Pancreatitis, immune-related	Grade 2 or 3	
Hold atezolizumab if radiologic findings or physical exam findings are suggestive of immune-related pancreatitis.
 
Note: If amylase/lipase \geq 2X ULN, refer to GI specialist and consider scan to evaluate for immune-mediated pancreatitis.
 
Refer patient to GI specialist.
 
Initiate treatment with 1–2 mg/kg/day intravenous methylprednisolone or equivalent and convert to 1–2 mg/kg/day oral prednisone or equivalent upon improvement.
 
If event resolves to grade 1 or better within 12 weeks, taper corticosteroids and resume atezolizumab according to the guidelines above.
 
Permanently discontinue atezolizumab if event does not resolve to grade 1 or better within 12 weeks. Patient may only resume treatment after consultation with the trial PI.
 
For recurrent events, permanently discontinue atezolizumab. Patient may not resume treatment, regardless of benefit.

	Grade 4	
Permanently discontinue atezolizumab. Patient may not resume treatment, regardless of benefit.
 
Refer patient to GI specialist.
 
Initiate treatment with 1–2 mg/kg/day intravenous methylprednisolone or equivalent and convert to 1–2 mg/kg/day oral prednisone or equivalent upon improvement.
 
If event does not improve within 48 hours after initiating corticosteroids, consider adding an immunosuppressive agent.

AE Management and Dose Interruption Guidelines for Specific Toxicities in Treatment		
Toxicity	Severity/ Duration	Management
		If event resolves to grade 1 or better, taper corticosteroids over \geq 1 month.
Pulmonary toxicity	All pulmonary events	Evaluate thoroughly for other commonly reported etiologies such as pneumonia/infection, lymphangitic carcinomatosis, pulmonary embolism, heart failure, chronic obstructive pulmonary disease (COPD), or pulmonary hypertension.
	Grade 1	
Continue atezolizumab and monitor closely.
 
Consider serial imaging (repeat imaging scan or x-ray 1-2 weeks later).
 
Consider patient referral to a pulmonary specialist.
 
For recurrent pneumonitis, treat as a grade 3 or 4 event.

	Grade 2	
Hold atezolizumab.
 
Refer patient to pulmonary and infectious disease specialists and consider bronchoscopy or bronchoscopic alveolar lavage (BAL).
 
Initiate treatment with 1–2 mg/kg/day oral prednisone or equivalent.
 
If event resolves to grade 1 or better within 12 weeks, taper corticosteroids and resume atezolizumab according to the guidelines above.
 
Permanently discontinue atezolizumab if event does not resolve to grade 1 or better within 12 weeks.
 
For recurrent events, treat as a Grade 3 or 4

AE Management and Dose Interruption Guidelines for Specific Toxicities in Treatment		
Toxicity	Severity/ Duration	Management
		event. Hold atezolizumab. Bronchoscopy or BAL is recommended. Initiate treatment with 1–2 mg/kg/day oral prednisone or equivalent. If event does not improve within 48 hours after initiating corticosteroids, consider adding an immunosuppressive agent. If event resolves to grade 1 or better, taper corticosteroids over \geq 1 month. For grade 3 AEs, patient may only resume treatment after consultation with the trial PI. For grade 4, patient cannot resume treatment, regardless of benefit.
	Grade 3 or 4	

6.2 Cobimetinib

Cobimetinib may be dose reduced in this study for drug-related toxicity. Management of certain AEs of particular concern for patients on cobimetinib plus atezolizumab are presented in 6.3. For other AEs, refer to general recommended dose modifications for cobimetinib (presented below, 6.2.1) and atezolizumab (6.1.1). Patients may temporarily suspend cobimetinib treatment for up to 84 days (12 weeks) if study drug-related toxicity requiring dose suspension is experienced. If cobimetinib is held because of AEs for $>$ 84 days, the patient will be discontinued from cobimetinib therapy.

Patients experiencing adverse events attributable to cobimetinib therapy may continue atezolizumab therapy while cobimetinib is held. Patients discontinued from cobimetinib therapy may continue atezolizumab therapy, and will be followed for safety and efficacy as specified in this protocol.

Dose interruptions for reasons other than toxicity, such as surgical procedures, may be allowed. The acceptable length of interruption will be at the discretion of the study PI in consultation with CTEP.

6.2.1 Recommended Cobimetinib Dose Modifications

In order to standardize the management of AEs, suggested treatment management algorithms for adverse events of particular concern for cobimetinib plus atezolizumab are

included in section 6.3. The following general dose modifications table for cobimetinib is for AEs not specified in the subsequent tables.

Grade (CTCAE) ^a	Recommended Cobimetinib Dose
Grade 1 or Grade 2 (tolerable)	No dose reduction. Maintain cobimetinib at a dose of 60 mg QD (3 tablets)
Grade 2 (intolerable) or Grade 3 or 4 (any) First appearance	Interrupt treatment until Grade \leq 1, restart treatment at 40 mg QD (2 tablets)
Second appearance	Interrupt treatment until Grade \leq 1, restart treatment at 20 mg QD (1 tablet)
Third appearance	Consider permanent discontinuation

CTCAE = Common Terminology Criteria for Adverse Events; NCI = National Cancer Institute; QD = once daily.

^a The intensity of clinical adverse events graded by NCI CTCAE v5.0.

Below is a table for cobimetinib dosing upon dose modification:

Dose level	Dose
0	60 mg QD 21 days out of 28 days
(-1)	40 mg QD, 21 days out of 28 days
(-2)	20 mg QD, 21 days out of 28 days

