Grade 2	
Hold atezolizumab and cobimetinib.
 
Initiate symptomatic treatment.
 
Suggested regimen:
 
Loperamide: Initiate dose with 4 mg, then 4 mg/6 hr around the clock, alternating with Lomotil.
 
Lomotil (diphenoxylate and atropine): 2 tablets (diphenoxylate 5 mg) every 6 hr around the clock
 
Continue Lomotil and loperamide until no loose stools for 24 hours.
 
If Grade ≤ 2 diarrhea persists after 48 hr total treatment

	
with Lomotil and loperamide, consider second-line agents (e.g., octreotide, budesonide, tincture of opium).
 
Patient referral to GI specialist is recommended.
 
For recurrent events or events that persist >5 days, initiate treatment with 1–2 mg/kg/day oral prednisone or equivalent.
 
If event resolves to grade 1 or better within 12 weeks, taper corticosteroids and resume atezolizumab and cobimetinib according to the guidelines above.
 
Permanently discontinue atezolizumab if event does not resolve to grade 1 or better within 12 weeks.
 
Resumption of atezolizumab may be considered, after consultation with the trial PI, in patients who are deriving benefit and have fully recovered from the immune-related event.

Grade 3	
Hold atezolizumab and cobimetinib.
 
Refer patient to GI specialist for evaluation and confirmatory biopsy.
 
Initiate treatment with 1–2 mg/kg/day intravenous methylprednisolone or equivalent and convert to 1–2 mg/kg/day oral prednisone or equivalent upon improvement.
 
If event resolves to grade 1 or better within 12 weeks, taper corticosteroids and restart atezolizumab at fixed dose and cobimetinib at 1 dose reduction once at baseline stool frequency.
 
Permanently discontinue atezolizumab and cobimetinib if event does not resolve to Grade 1 or better within 12 weeks.
 
Resumption of atezolizumab and cobimetinib may be considered, after consultation with the trial PI, in patients who are deriving benefit and have fully recovered from the immune-related event.

Grade 4	Permanently discontinue atezolizumab and cobimetinib.

	
Patient may not resume treatment, regardless of benefit.
 
Refer patient to GI specialist for evaluation and confirmation biopsy.
 
Initiate treatment with 1–2 mg/kg/day intravenous methylprednisolone or equivalent and convert to 1–2 mg/kg/day oral prednisone or equivalent upon improvement.
 
Consider TNF antagonists for refractory diarrhea.

--	--

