GI = gastrointestinal; IV = intravenous; LLN = lower limit of normal; NSAID = nonsteroidal anti-inflammatory drug; TNF = tumor necrosis factor.

Amylase and/or lipase increased	Management
Grade 1	
Continue atezolizumab and cobimetinib.
 
Monitor amylase and lipase prior to dosing.

Grade 2	
Continue atezolizumab and cobimetinib.
 
Monitor amylase and lipase weekly.
 
For prolonged elevation (e.g., >3 weeks), consider treatment with 10 mg/day oral prednisone or equivalent.

Grade 3 or 4	
Hold atezolizumab and cobimetinib.
 
Refer patient to gastrointestinal (GI) specialist.
 
Monitor amylase and lipase every other day.
 
If no improvement, consider treatment with 1–2 mg/kg/day oral prednisone or equivalent.
 
If event resolves to grade 1 or better within 12 weeks, taper corticosteroids and resume atezolizumab according to the guidelines above.
 
Permanently discontinue atezolizumab if event does not resolve to grade 1 or better within 12 weeks.
 
For recurrent events, permanently discontinue atezolizumab.

HEPATOTOXICITY

Hepatotoxicity has been associated with the administration of atezolizumab and cobimetinib. Eligible patients must have adequate liver function, as manifested by measurements of total bilirubin and hepatic transaminase, and liver function will be monitored throughout study treatment.

While in this study, patients presenting with right upper-quadrant abdominal pain and/or unexplained nausea or vomiting should have liver function tests (LFTs) performed immediately and reviewed before administration of the next dose of study drug.

If LFTs increase, neoplastic, concurrent medications, viral hepatitis, and toxic etiologies should be considered and addressed, as appropriate. Imaging of the liver, gall bladder, and biliary tree should be performed to rule out neoplastic or other causes for the increased LFTs. Anti-nuclear antibody, perinuclear anti-neutrophil cytoplasmic antibody, anti-liver kidney microsomal antibodies, and anti-smooth muscle antibody tests should be considered.

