Right upper-quadrant abdominal pain and/or unexplained nausea or vomiting	Risk of immune-mediated hepatitis. LFTs should be performed immediately, and LFTs should be reviewed before administration of the next dose of study drug. For patients with elevated LFTs, concurrent medication, viral hepatitis, and toxic or neoplastic etiologies should be considered and addressed, as appropriate. Symptoms of abdominal pain associated with elevations of amylase and lipase, suggestive of pancreatitis, have been associated with the administration of atezolizumab. The differential diagnosis of acute abdominal pain should also include pancreatitis , as described below.
Grade 1 hepatic event	Continue atezolizumab and cobimetinib. Monitor LFTs until values resolve to within normal limits.
Grade 2 hepatic event, ≤ 5 days	Continue atezolizumab and cobimetinib. Monitor LFTs more frequently until values resolve to baseline values.

Grade 2 hepatic event, >5 days	
Hold atezolizumab and cobimetinib.
 
Initiate treatment with 1–2 mg/kg/day oral prednisone or equivalent.
 
If event resolves to grade 1 or better within 12 weeks, taper corticosteroids and resume atezolizumab and cobimetinib at 1 dose reduction.
 
Permanently discontinue atezolizumab if event does not resolve to Grade 1 or better within 12 weeks. Resumption of cobimetinib may be considered after discussion with the sponsor provided there is evidence of clinical benefit and continued therapy is of interest.

Grade 3 or 4 hepatic event	
Permanently discontinue atezolizumab and hold cobimetinib.
 
Consider patient referral to GI specialist for evaluation and liver biopsy to establish etiology of hepatic injury.
 
Initiate treatment with 1–2 mg/kg/day oral prednisone or equivalent.
 
If event does not improve within 48 hours after initiating corticosteroids, consider adding an immunosuppressive agent.
 
If event resolves to grade 1 or better, taper corticosteroids over ≥ 1 month.
 
Resumption of cobimetinib may be considered after discussion with the sponsor provided there is evidence of clinical benefit and continued therapy is of interest.

IV = intravenous; LFT = liver function test; q4w = every 4 weeks; TNF = tumor necrosis factor; ULN = upper limit of normal.

DERMATOLOGIC TOXICITY

Treatment-emergent rash has been associated with atezolizumab and cobimetinib. The majority of the cases of rash were mild in severity and self-limited, with or without pruritus.

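### The Section 6.2.1 cobimetinib table fixes restart doses in mg by an undefined count, so a patient already at 40 mg after a Section 6.3 reduction can, read literally, restart with no reduction

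*Combined protocol and SAP*

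**What the plan says.** Section 6.2 allows cobimetinib to be reduced: "Cobimetinib may be dose reduced in this study for drug-related toxicity". It sends events of particular concern to Section 6.3 and all others to Section 6.2.1. Section 6.2.1 confirms the split: "The following general dose modifications table for cobimetinib is for AEs not specified in the subsequent tables".

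The Section 6.2.1 table then works in fixed amounts:

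- Grade 1 or tolerable Grade 2: "No dose reduction. Maintain cobimetinib at a dose of 60 mg QD (3 tablets").
- Intolerable Grade 2 or any Grade 3–4, first appearance: interrupt to Grade 1 or better, then "restart treatment at 40 mg QD (2 tablets").
- Second appearance: restart at 20 mg. Third appearance: consider stopping for good.

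Directly below, a ladder lists level 0 (60 mg), level −1 (40 mg) and level −2 (20 mg).

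Section 6.3 is mostly relative. Grade 3 diarrhea, for example, says "restart atezolizumab at fixed dose and cobimetinib at 1 dose reduction once at baseline stool frequency", and a Grade 2 hepatic event lasting more than 5 days says "resume atezolizumab and cobimetinib at 1 dose reduction".

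**The concern.** The two sections use different rules for the same drug, and nothing joins them. Section 6.3 events lie outside the Section 6.2.1 table, so a later event such as Grade 3 fatigue is naturally that table's first appearance, whatever dose the patient is taking by then. For a patient whom Section 6.3 has already brought down to 40 mg, the printed instruction is to resume the dose on which the new toxicity arose. The first row has a related fault: it tells the site to hold a patient at 60 mg who may no longer be on 60 mg.

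A site that counts Section 6.3 reductions would restart the same patient at 20 mg. The gap therefore bears on the safety of Arm B patients and on consistent dosing behind the safety and tolerability objective (Section 1.2.3). Section 6.2.1 itself gives standardized management of adverse events as its aim.

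**Working it through.** The plan states no figure to reproduce. The check traces the rule.

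**Step 1. Can a patient be below 60 mg before a first Section 6.2.1 event?** Fourteen rows of Section 6.3 hold cobimetinib without ordering a permanent stop.

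- Eight step down from the current dose: Grade 3 diarrhea, Grade 2 hepatic event over 5 days, Grade 3 rash, Grade 2 pulmonary event, Grade 2–3 serous retinopathy, asymptomatic LVEF decrease, symptomatic LVEF decrease, and Grade 4 CPK.
- One restarts at the previous dose: Grade 3 CPK.
- Five state no cobimetinib restart dose of their own: Grade 2 diarrhea ("resume atezolizumab and cobimetinib according to the guidelines above"), Grade 3–4 amylase or lipase ("If event resolves to grade 1 or better within 12 weeks, taper corticosteroids and resume atezolizumab according to the guidelines above", which names atezolizumab only), Grade 3–4 hepatic event, Grade 3–4 pulmonary event, and symptomatic eye toxicity.

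The sum is 8 + 1 + 5 = 14. None sets a fixed restart dose regardless of the current one. So yes: one step-down row puts a patient at 40 mg, and two put a patient at 20 mg.

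**Step 2. Apply Section 6.2.1 literally and compare it with one step on the ladder.**

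| Dose at onset | First appearance, as printed | Second appearance, as printed | One level down |
|---|---|---|---|
| 60 mg | 40 mg | – | 40 mg |
| 40 mg | 40 mg (no change) | 20 mg | 20 mg |
| 20 mg | 40 mg (higher) | 20 mg (no change) | consider stopping |

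At 60 mg with a first appearance the two rules agree. They part once a Section 6.3 reduction has come first.

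**Step 3. Does the meaning of *appearance* settle it?** Take a patient reduced to 40 mg for Grade 3 diarrhea who then has a first Grade 3 fatigue.

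- Counted per toxicity term: first appearance, restart at 40 mg.
- Counted per patient within Section 6.2.1: first appearance, restart at 40 mg.
- Counted per patient with Section 6.3 reductions included: second appearance, restart at 20 mg.

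Only the third reading is free of the fault. The protocol does not choose among them, and its scope sentence leans toward the first two.

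**Step 4. Size for one patient.** A course is 21 dosing days. At 40 mg: 40 × 21 = 840 mg. One level down: 20 × 21 = 420 mg.

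**The case against.** The best answer is that the intent is plain. The ladder sits directly under the table, so first, second and third appearance read as level −1, level −2 and consider stopping. The 60 mg in the first row suggests that the amounts were written for a patient at level 0. Section 6.2 speaks only of reducing. The serous retinopathy and Grade 4 CPK rows follow the same pattern of two reductions and then a stop. The doses are labelled as recommended. Section 13.1 provides weekly review by the lead team and bimonthly calls with sites, Section 12.2 adds at least monthly calls, and Section 5.3 lets the physician stop treatment.

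The argument about intent stands: stepwise reduction was meant. But the ladder only lists levels. No sentence there or elsewhere says to step down from the current level or to count Section 6.3 reductions. The calls and reviews may catch a case, but they supply no dose.

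Two stronger readings are tempting and are not supported.

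- **A rise from 20 to 40 mg.** The table allows it on paper (Step 2), but it runs against Section 6.2 and is unlikely in practice.
- **A large share of patients misdosed.** Section 2.2.2.2 reports Grade 3–4 hyponatremia (9.6%), fatigue (8.7%), anemia (7.8%) and hypokalemia (6.1%) on cobimetinib monotherapy. None of these has a Section 6.3 row. On 115 patients they are 11, 10, 9 and 7, so at least one occurred in between 11/115 = 9.6% (full overlap) and (11 + 10 + 9 + 7)/115 = 37/115 = 32.2% (no overlap). A reader might take this as the share affected. It is not. It counts single events of any cause, pooled over doses and schedules, whereas the fault needs a Section 6.3 reduction first and a Section 6.2.1 event afterwards. It shows only that the table would be used.

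**Conclusion.** The gap in the wording is real and the point holds, at low priority. As printed, an Arm B patient at 40 mg after a Section 6.3 step-down who has a first Section 6.2.1 event restarts at 40 mg, and the 60 mg maintenance row does not fit any reduced patient. This rests on counting appearances per term or within the Section 6.2.1 table. If each Section 6.3 reduction counts as an appearance, no patient is affected.

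The number affected cannot be derived, because the documents do not give the share of patients reduced under Section 6.3. It is probably small. Only Arm B is exposed (38 evaluable patients planned), two events must occur in sequence, and the longer of the two assumed median PFS values is only 4 months (Section 13.2).

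That the text is silent is certain. How often that silence would change a dose is not known. The PFS comparison, its alpha and its power do not depend on this table.

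**What to change.** In Section 6.2.1, replace the fixed amounts for intolerable Grade 2 or Grade 3–4 events with: *Interrupt until Grade ≤ 1, then restart one dose level below the patient's current assigned dose level (60 to 40 mg, 40 to 20 mg), counting reductions made under Section 6.3. If already at 20 mg, consider permanent discontinuation.* Change the first row to: *No dose reduction. Maintain current dose level.* Add that a temporary reduction for a CYP3A inhibitor, which Section 8.1.2 allows, does not change the assigned level. The count of appearances is then no longer needed.

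Leave the Section 6.3 rows as they are for this purpose. In particular, keep the mandatory permanent stops when Grade 2–3 serous retinopathy or Grade 4 CPK elevation recurs after two reductions. Copying the softer *consider* wording into those rows would weaken them.

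The cost is a wording amendment to one table and a memo to sites, with no extra patients or procedures. The downside is that some patients would reach 20 mg, or stop cobimetinib, slightly earlier than under a fixed 40 mg restart.

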6.3 Management of Cobimetinib plus Atezolizumab–Associated Adverse Events of particular concern

In general, patients discontinued from combination therapy due to intolerance or adverse events that are attributable to only one of the two drug therapies may continue monotherapy with the therapy that is not causing the adverse event. For example, a patient removed from cobimetinib therapy after developing retinal vein occlusion may continue atezolizumab monotherapy. Below, recommended management of specific adverse events of particular concern with combination therapy are provided.

GASTROINTESTINAL TOXICITY

Diarrhea and colitis have been associated with the administration of cobimetinib plus atezolizumab. Diarrhea can frequently be managed with anti-diarrheal agents but can also progress to clinically significant dehydration and/or electrolyte imbalances with effects on other organs, possibly resulting in renal, hepatic, and/or cardiac failure. Patients should be instructed to promptly contact the investigators if they develop diarrhea. Investigators should treat diarrhea and intervene promptly for patients who appear to be at increased risk of developing significant dehydration, electrolyte imbalances, and/or multi-organ failure. Patients should receive maximum supportive care per institutional guidelines.

Diarrhea or colitis	Management
Any grade	
Patients should be advised to inform the investigator if any diarrhea occurs, even if it is mild.
 
All events of diarrhea or colitis should be thoroughly evaluated for other more common etiologies.
 
For events of significant duration or magnitude or associated with signs of systemic inflammation or acute-phase reactants (e.g., increased CRP, platelet count, or bandemia): Perform sigmoidoscopy (or colonoscopy, if appropriate) with colonic biopsy, with three to five specimens for standard paraffin block to check for inflammation and lymphocytic infiltrates to confirm colitis diagnosis.

Grade 1	
Continue atezolizumab and cobimetinib.
 
Initiate symptomatic treatment.
 
Suggested regimen:
 
Loperamide: Initiate dose with 4 mg, then 4 mg/6 hr around the clock, alternating with Lomotil.
 
Lomotil (diphenoxylate and atropine): 2 tablets (diphenoxylate 5 mg) every 6 hr around the clock
 
Continue Lomotil and loperamide until no loose stools for 24 hours
 
Endoscopy is recommended if symptoms persist for >7 days.
 
Monitor closely.

Grade 2	
Hold atezolizumab and cobimetinib.
 
Initiate symptomatic treatment.
 
Suggested regimen:
 
Loperamide: Initiate dose with 4 mg, then 4 mg/6 hr around the clock, alternating with Lomotil.
 
Lomotil (diphenoxylate and atropine): 2 tablets (diphenoxylate 5 mg) every 6 hr around the clock
 
Continue Lomotil and loperamide until no loose stools for 24 hours.
 
If Grade ≤ 2 diarrhea persists after 48 hr total treatment

	
with Lomotil and loperamide, consider second-line agents (e.g., octreotide, budesonide, tincture of opium).
 
Patient referral to GI specialist is recommended.
 
For recurrent events or events that persist >5 days, initiate treatment with 1–2 mg/kg/day oral prednisone or equivalent.
 
If event resolves to grade 1 or better within 12 weeks, taper corticosteroids and resume atezolizumab and cobimetinib according to the guidelines above.
 
Permanently discontinue atezolizumab if event does not resolve to grade 1 or better within 12 weeks.
 
Resumption of atezolizumab may be considered, after consultation with the trial PI, in patients who are deriving benefit and have fully recovered from the immune-related event.

Grade 3	
Hold atezolizumab and cobimetinib.
 
Refer patient to GI specialist for evaluation and confirmatory biopsy.
 
Initiate treatment with 1–2 mg/kg/day intravenous methylprednisolone or equivalent and convert to 1–2 mg/kg/day oral prednisone or equivalent upon improvement.
 
If event resolves to grade 1 or better within 12 weeks, taper corticosteroids and restart atezolizumab at fixed dose and cobimetinib at 1 dose reduction once at baseline stool frequency.
 
Permanently discontinue atezolizumab and cobimetinib if event does not resolve to Grade 1 or better within 12 weeks.
 
Resumption of atezolizumab and cobimetinib may be considered, after consultation with the trial PI, in patients who are deriving benefit and have fully recovered from the immune-related event.

Grade 4	Permanently discontinue atezolizumab and cobimetinib.

	
Patient may not resume treatment, regardless of benefit.
 
Refer patient to GI specialist for evaluation and confirmation biopsy.
 
Initiate treatment with 1–2 mg/kg/day intravenous methylprednisolone or equivalent and convert to 1–2 mg/kg/day oral prednisone or equivalent upon improvement.
 
Consider TNF antagonists for refractory diarrhea.

--	--

GI = gastrointestinal; IV = intravenous; LLN = lower limit of normal; NSAID = nonsteroidal anti-inflammatory drug; TNF = tumor necrosis factor.

Amylase and/or lipase increased	Management
Grade 1	
Continue atezolizumab and cobimetinib.
 
Monitor amylase and lipase prior to dosing.

Grade 2	
Continue atezolizumab and cobimetinib.
 
Monitor amylase and lipase weekly.
 
For prolonged elevation (e.g., >3 weeks), consider treatment with 10 mg/day oral prednisone or equivalent.

Grade 3 or 4	
Hold atezolizumab and cobimetinib.
 
Refer patient to gastrointestinal (GI) specialist.
 
Monitor amylase and lipase every other day.
 
If no improvement, consider treatment with 1–2 mg/kg/day oral prednisone or equivalent.
 
If event resolves to grade 1 or better within 12 weeks, taper corticosteroids and resume atezolizumab according to the guidelines above.
 
Permanently discontinue atezolizumab if event does not resolve to grade 1 or better within 12 weeks.
 
For recurrent events, permanently discontinue atezolizumab.

HEPATOTOXICITY

Hepatotoxicity has been associated with the administration of atezolizumab and cobimetinib. Eligible patients must have adequate liver function, as manifested by measurements of total bilirubin and hepatic transaminase, and liver function will be monitored throughout study treatment.

While in this study, patients presenting with right upper-quadrant abdominal pain and/or unexplained nausea or vomiting should have liver function tests (LFTs) performed immediately and reviewed before administration of the next dose of study drug.

If LFTs increase, neoplastic, concurrent medications, viral hepatitis, and toxic etiologies should be considered and addressed, as appropriate. Imaging of the liver, gall bladder, and biliary tree should be performed to rule out neoplastic or other causes for the increased LFTs. Anti-nuclear antibody, perinuclear anti-neutrophil cytoplasmic antibody, anti-liver kidney microsomal antibodies, and anti-smooth muscle antibody tests should be considered.

Right upper-quadrant abdominal pain and/or unexplained nausea or vomiting	Risk of immune-mediated hepatitis. LFTs should be performed immediately, and LFTs should be reviewed before administration of the next dose of study drug. For patients with elevated LFTs, concurrent medication, viral hepatitis, and toxic or neoplastic etiologies should be considered and addressed, as appropriate. Symptoms of abdominal pain associated with elevations of amylase and lipase, suggestive of pancreatitis, have been associated with the administration of atezolizumab. The differential diagnosis of acute abdominal pain should also include pancreatitis , as described below.
Grade 1 hepatic event	Continue atezolizumab and cobimetinib. Monitor LFTs until values resolve to within normal limits.
Grade 2 hepatic event, ≤ 5 days	Continue atezolizumab and cobimetinib. Monitor LFTs more frequently until values resolve to baseline values.

Grade 2 hepatic event, >5 days	
Hold atezolizumab and cobimetinib.
 
Initiate treatment with 1–2 mg/kg/day oral prednisone or equivalent.
 
If event resolves to grade 1 or better within 12 weeks, taper corticosteroids and resume atezolizumab and cobimetinib at 1 dose reduction.
 
Permanently discontinue atezolizumab if event does not resolve to Grade 1 or better within 12 weeks. Resumption of cobimetinib may be considered after discussion with the sponsor provided there is evidence of clinical benefit and continued therapy is of interest.

Grade 3 or 4 hepatic event	
Permanently discontinue atezolizumab and hold cobimetinib.
 
Consider patient referral to GI specialist for evaluation and liver biopsy to establish etiology of hepatic injury.
 
Initiate treatment with 1–2 mg/kg/day oral prednisone or equivalent.
 
If event does not improve within 48 hours after initiating corticosteroids, consider adding an immunosuppressive agent.
 
If event resolves to grade 1 or better, taper corticosteroids over ≥ 1 month.
 
Resumption of cobimetinib may be considered after discussion with the sponsor provided there is evidence of clinical benefit and continued therapy is of interest.

IV = intravenous; LFT = liver function test; q4w = every 4 weeks; TNF = tumor necrosis factor; ULN = upper limit of normal.

DERMATOLOGIC TOXICITY

Treatment-emergent rash has been associated with atezolizumab and cobimetinib. The majority of the cases of rash were mild in severity and self-limited, with or without pruritus.


A dermatologist should evaluate persistent and/or severe rash or pruritus. A biopsy should be considered unless contraindicated.
 
Dermatologic Toxicity/Rash (e.g., maculo-papular or purpura)
	
Management

Grade 1
	
Continue atezolizumab and cobimetinib
 
Initiate symptomatic therapy with antihistamine PRN.
 
Consider topical steroids and/or other symptomatic therapy (e.g., antihistamines).
 
For acneiform rash, consider topical corticosteroids (hydrocortisone 2.5%, alclometasone) and oral antibiotics (minocycline, doxycycline, or antibiotics covering skin flora) BID for at least 4 weeks.

Grade 2
	
Continue atezolizumab and cobimetinib.
 
Consider consultation with a dermatologist.
 
Administer topical steroids.
 
Consider higher potency topical steroids if rash does not improve.
 
For acneiform rash, topical corticosteroids (hydrocortisone 2.5%, alclometasone) and oral antibiotics (minocycline, doxycycline, or antibiotics covering skin flora) BID for at least the first 6 weeks.

Grade 3	
Hold atezolizumab and cobimetinib.
 
Consult dermatologist.
 
Administer oral prednisone 10 mg or equivalent if the rash is at least possibly attributable to the atezolizumab therapy. If the event does not improve within 48-72 hours, increase dose to 1–2 mg/kg/day or equivalent.
 
Restart atezolizumab at fixed dose and cobimetinib at 1 dose reduction if rash resolves to \leq tolerable grade 2, and systemic dose is < 10 mg oral prednisone equivalent per day.
 
For acneiform rash, consider continuation of topical corticosteroids 2.5%, alclometasone) and oral antibiotics (minocycline, doxycycline or antibiotics covering skin flora) when restarting cobimetinib.

Grade 4	
Permanently discontinue atezolizumab and cobimetinib. Patient may not resume treatment, regardless of benefit. Manage as above.

Persistent and/or severe rash or pruritus, any grade	
A dermatologist should evaluate the event. A biopsy should be performed unless contraindicated.

BID = twice daily; BSA = body surface area; PRN = as needed.

PULMONARY TOXICITY

Mild-to-moderate events of pneumonitis have been reported with atezolizumab and cobimetinib. All pulmonary events should be thoroughly evaluated for other commonly reported etiologies such as pneumonia/infection, lymphangitic carcinomatosis, pulmonary embolism, heart failure, chronic obstructive pulmonary disease, or pulmonary hypertension:

- Measurement of oxygen saturation (i.e., arterial blood gas)
- High-resolution computed tomography (CT) scan of the chest
- Bronchoscopy with bronchoalveolar lavage and biopsy (if clinically feasible)
- Pulmonary function tests (diffusion capacity of the lung for carbon monoxide)
- Pulmonary function testing with a pulmonary embolism protocol

Patients will be assessed for pulmonary signs and symptoms throughout the study. Patients will also have CT scans of the chest at every tumor assessment. Chest CT should be reviewed for pulmonary toxicities as well as for disease status.

All pulmonary events	
Evaluate thoroughly for other commonly reported etiologies such as pneumonia/infection, lymphangitic carcinomatosis, pulmonary embolism, heart failure, chronic obstructive pulmonary disease (COPD), or pulmonary hypertension.

----------------------	---

Grade 1	
Continue atezolizumab and cobimetinib and monitor closely.
 
Consider serial imaging (repeat imaging scan or x-ray 1-2 weeks later).
 
Consider patient referral to a pulmonary specialist.
 
For recurrent pneumonitis, treat as a grade 3 or 4 event.

Grade 2	
Hold atezolizumab and cobimetinib.
 
Refer patient to pulmonary and infectious disease specialists and consider bronchoscopy or bronchoscopic alveolar lavage (BAL).
 
Initiate treatment with 1–2 mg/kg/day oral prednisone or equivalent.
 
If event resolves to grade 1 or better within 12 weeks, taper corticosteroids and resume atezolizumab at fixed dose and cobimetinib at 1 dose reduction if GGO/infiltrates improving.
 
Permanently discontinue atezolizumab and cobimetinib if event does not resolve to grade 1 or better within 12 weeks.
 
For recurrent events, treat as a Grade 3 or 4 event.

Grade 3 or 4	
Hold atezolizumab and cobimetinib.
 
Bronchoscopy or BAL is recommended.
 
Initiate treatment with 1–2 mg/kg/day oral prednisone or equivalent.
 
If event does not improve within 48 hours after initiating corticosteroids, consider adding an immunosuppressive agent.
 
If event resolves to grade 1 or better, taper corticosteroids over ≥ 1 month.
 
For grade 3 AEs, patient may only resume treatment after consultation with the trial PI.
 
For grade 4, patient cannot resume treatment, regardless of benefit.

POTENTIAL EYE TOXICITY

An ophthalmologist should evaluate visual complaints.

Uveitis or episcleritis and other immune-mediated ocular disease may be associated with atezolizumab and may be treated with topical corticosteroid eye drops. Atezolizumab should be permanently discontinued for immune-mediated ocular disease that is unresponsive to local immunosuppressive therapy.

Serous retinopathy have been associated with cobimetinib.

Eye Toxicities	Management
Symptomatic eye toxicity (autoimmune uveitis, iritis or episcleritis)	
Hold atezolizumab and cobimetinib.
 
Consult ophthalmologist and start topical corticosteroid eye drops.
 
Consider starting prednisone 60 mg/day or equivalent.
 
Taper steroids over \geq 1 month once symptoms improve to Grade 0/1 (asymptomatic).
 
Atezolizumab may be restarted following resolution of the events with careful monitoring for recurrence.
 
Permanently discontinue atezolizumab for immune-mediated ocular disease that is unresponsive to immunosuppressive therapy.

Retinal vein occlusion Any grade	If RVO (any grade) is diagnosed, cobimetinib dosing should be permanently discontinued and RVO treated per institutional guidelines. Atezolizumab therapy may be continued.
Serous retinopathy Severity grade assessment based on NCI CTCAE v 5.0 “Eye Disorders – Other” scale. Grade 1: Asymptomatic or mild symptoms; clinical or diagnostic observations only; intervention not indicated	
Continue atezolizumab and cobimetinib without dose change.
 
Continue ophthalmology follow-up as clinically indicated.

